This study is a randomized open label clinical trial that will compare the safety and efficacy of pyronaridine-artesunate and artemether-lumefantrine in the treatment of malaria among children aged 3 to 144 months who have microscopically confirmed symptomatic *Plasmodium falciparum* malaria. The study will be carried out at the Oni Memorial Children's Hospital, [name]. One hundred and sixty-two children between 3 and 144 months who meet the inclusion criteria will be enrolled after obtaining written or witnessed signed informed consent from the parents or guardian. Details obtained from the enrolee will be entered into a case record form specifically designed for the purpose of accurate documentation. A detailed history and physical examination will be carried out on each enrolee. Finger prick blood samples will be taken from each enrolee for thick blood smear for malaria parasite, haematocrit and blood spots on filter paper. Five millilitres of venous blood will be taken from an arm vein for baseline liver function tests, creatinine and random blood glucose on days 0, 3, 7 and 28.

Enrolees will be randomized into one of two groups. Group one will receive pyronaridine-artesunate while group two will receive artemether-lumefantrine at standard doses. Enrolees will be seen daily from days 0-3, and on days 7, 14, 21 and 28. Study drugs will be administered supervised at standard dosage on days 0, 1, and 2. History taking, physical examination and blood smears will be done at each contact time. Special attention will be paid to adverse effects.

Parasite clearance time, fever clearance time and cure rates will be compared between the two groups. The data collected from the participants will be entered into Epi info version 6 databases and then transferred to SPSS Statistics Software version 20 for statistical analysis.

INTRODUCTION

Background of the study

Malaria is an important protozoan infection which poses a major health problem in the world today.[1] The infection is endemic in most parts of the tropics, including Nigeria with a greater percentage of malaria incidence and deaths occurring amongst pregnant women and children under five years of age.[2] In Nigeria, malaria is the commonest reason for outpatient clinic attendance in childhood and is responsible for about 20 % of childhood deaths.[3] Malaria is the only vector borne disease placed on the World Health Organization's disability adjusted life years (DALYS) list.[4] Of the approximately 3.4 billion people worldwide who are exposed to malaria yearly, the World Health Organization (WHO) states that there were about 219 million cases of symptomatic malaria in 2016.[5]

Although, mortality rates from malaria seem to have fallen globally and in the Africa region due to effective control measures, the disease continues to be a major threat to childhood health and development. In 2016 there were 445000 deaths with 80% of these occurring in children under 5 years and pregnant women.[5] Chloroquine (CQ) and sulfadoxine-pyrimethamine (SP) which were once very effective against the malaria parasite, have been replaced in many malaria-endemic countries by artemisinin-based combination therapies as first line drugs due to the emergence of resistance to these monotherapies in the malaria parasite following WHO recommendations[6]. Increasing parasite resistance to these old drugs and failure of malaria treatment with these single agents in many endemic countries of Africa led to a widespread promotion of artemisinin-based combination therapy (ACT) as a strategy for effective management of *Plasmodium falciparum* malaria. The World Health Organization (WHO) in 2001 recommended that malaria endemic countries change their treatment policies and adopt combination therapy, and in particular artemisinin-based combination therapy as the first-line antimalarial treatment.[1]

The artemisinins act by inhibiting *Plasmodium falciparum* encoded sarcoplasmic endoplasmic reticulum calcium ATPase. They inhibit development of gametocytes thus reducing transmission.[7] Gametocytes, the sexual stages of the malaria parasite, do not cause clinical disease but are vital to the maintenance of malaria transmission cycle. These gametocytes are present in symptomatic and asymptomatic parasitemic individuals.[7] The WHO defines artemisinin-based combination therapy for malaria as the simultaneous use of at least two efficacious schizonticidal drugs one of which is an artemisinin derivative. The two or more drugs must have different mechanisms of action and thus different biochemical targets in the parasite.[8] It is important that the two or more constituent drugs are efficacious and are used at individual full dosages. Artemisinin-based combination therapies (ACTs) are now the first-line treatment for acute uncomplicated malaria globally. They are more effective than the non-artemisinin-based combination or monotherapies, as they lead to rapid parasite clearance, hasten clinical recovery and reduce the chances of development of drug resistance in the parasite.[1]

Artemether-lumefantrine (AL) is the first fixed - dose ACT to be pre-qualified by the WHO and the most commonly used ACT as first-line drug for the treatment of uncomplicated falciparum malaria in sub-Saharan Africa.[6, 8]. It has also been extensively studied in Nigeria.[9-11] Artesunate-amodiaquine (ASAQ) the second most widely used ACT globally after artemether-lumefantrine is also currently used as a first line treatment in some countries in sub-Saharan Africa.[12-14] However, ASAQ is disadvantaged by the variability in dosing regimens between the different formulations of ASAQ.[15, 16] Dihydroartemisinin-piperaquine (DP) is another ACT that has been recommended by the WHO for use in the treatment of acute uncomplicated malaria.[17] However, DP is not widely used in sub-Saharan Africa compared to AL as its recommendation by the WHO is more recent.[1] Dihydroartemisinin-piperaquine has the advantage of daily dosing and does not require taking it with meal. The long half-life of piperaquine confers on DP a longer post treatment chemoprophylaxis when compared with AL.[18]

There are limitations to the use of AL which is the commonly used ACT in Nigeria. These include high number of dosing (six) which is not convenient and the need to give the drug with fatty food for optimal absorption of lumefantrine because of its high lipophilic property.[19] Pyronaridine, a Mannich base 1-aza-acridine structurally related to mepacrine and amopyroquine, one of the earliest synthetic antimalarial drugs, was first developed in China over 30 years ago. It has been used as monotherapy in parts of Asia and China.[20] Pyronaridine, is a benzonaphthyridine derivative that is active against *Plasmodium falciparum* and *Plasmodium vivax*.[21, 22]¹⁴

Pyronaridine-Artesunate (PA) is a novel fixed dose ACT drug that received a Positive Opinion through Article 58 from the **European Medicine Agency¹ (EMA)**. This Positive Opinion is a stringent regulatory review and approval granted for a specific group of drugs that will not be marketed in Europe. This rigorous review process is performed in conjunction with the WHO. At the time of the Positive Opinion (registration) PA also obtained WHO prequalification status. Pyramax received approval with EMA for the treatment of acute uncomplicated *P. falciparum* and *P. vivax* malaria. Subsequent EMA approvals have been granted for repeated dosing and for the paediatric formulation of granules in sachets. pyronaridine-artesunate has been found to have good efficacy and tolerability and is cost effective.[23-26] Like DP, pyronaridine-artesunate has a daily dosing regimen and can be taken with or without meals.[23] The studies conducted so far on the efficacy and tolerability of PA showed that other ACTs were not superior to it and there were strong recommendations that PA should be included as a standard antimalarial treatment.[27] The most commonly reported adverse effects were headache, eosinophilia, neutropenia, anaemia, increased platelet count, vomiting, abdominal pain, bradycardia, short lasting transaminase increases and hypoglycaemia.¹⁶ Other studies reported vomiting which may be due to its bitter taste, nausea, loss of appetite and cough.[27] More recent studies provide increasing evidence on the safety of Pyramax.[28, 29]

1 RATIONALE FOR THE STUDY

The World Health Organization currently recommends the use of one of five different artemisinin-based combination therapies (ACTs) for the treatment of acute uncomplicated *falciparum* malaria [1]. Studies conducted on pyronaridine-artesunate (Pyramax™ Shin Poong) showed that it compared well in terms of efficacy and safety with other ACTs. EMA granted positive opinion through Article 58 to Pyramax tablet in 2013 and to Pyramax granules in 2015, this stringent regulatory authority recognition confirms that Pyramax can be used in malaria patients and, in particular, in African children. However, additional studies are needed to confirm, in parallel to the launch of Pyramax, the good safety and efficacy observed in the Phase III program and in the peri-approval (WANECAM) study. The WHO is however yet to make a statement on the unconditional inclusion of pyronaridine-artesunate in the treatment guidelines, which may not be unconnected with limited amount of data available for a new product. Hence the more the observations recorded across different malaria endemic countries and in real life scenarios the greater the degree of confidence on the safety of the drug. This will enhance the possibility of having a greater role in the management of uncomplicated malaria.

The need for a cost effective and user friendly antimalarial with good efficacy and tolerability is highly desirable to expand the number of ACTs in Nigeria and the need to continue efforts to optimize efficacy, tolerability, costs, and treatment regimens has led to this clinical trial. Whereas the therapeutic and efficacy studies are often used to select ACTs for programmatic deployment, the National Malaria Elimination Programme (NMEP) in Nigeria has restructured and streamlined the conduct of **Therapeutic Efficacy Studies (TES)** restricting each cycle to just about 3-4 sentinel sites per year. Under the current arrangement, Pyronaridine-artesunate will not be included in the country's 2018 TES. A TES efficacy study conducted that is well aligned with the national TES protocol will provide important opportunity for expanding the use of pyronaridine-artesunate in Nigeria.

It is also important to continue to assess the efficacy of AL, the ACT of choice in Nigeria in order to detect early loss of efficacy as the country is an endemic region for malaria. In the results of the WANECAM study, the efficacy PCR corrected (recrudescence of the initial infection) is the same between Pyramax and AL, while PCR uncorrected (new infection) is different and Pyramax is better than AL. In addition, the safety and efficacy of pyronaridine-artesunate in children less than 20kg shall be studied, especially in children under 1 year of age which this study intends to cover.

2 OBJECTIVES

The aim of the study is to compare the safety and efficacy of Pyronaridine-Artesunate (PA) and Artemether-Lumefantrine (AL) in children aged between 3 months and 12 years with acute uncomplicated malaria in south-west Nigeria.

2.1 SPECIFIC OBJECTIVES

1. Primary:

To determine the comparative efficacy of pyronaridine-artesunate and artemether-lumefantrine in the treatment of acute uncomplicated malaria in children in south-west Nigeria.

2. Secondary:

- i. To compare the efficacy and safety (crude – ACPR) of pyronaridine-artesunate and artemether-lumefantrine in the treatment of acute uncomplicated malaria in children in south-west Nigeria
- ii. To determine and compare the parasite clearance time and the fever clearance time of pyronaridine-artesunate and artemether-lumefantrine in the treatment of acute uncomplicated malaria in children in south-west Nigeria
- iii. To determine and compare gametocyte carriage between pyronaridine-artesunate and artemether-lumefantrine during treatment of acute uncomplicated malaria in children in south-west Nigeria
- iv. To compare the PCR Corrected cure rates of pyronaridine-artesunate and artemether-lumefantrine in the treatment of acute uncomplicated malaria in children in south-west Nigeria

3 INVESTIGATION PLAN

3.1 Study Design

3.2 This is a randomized open label trial that will compare the safety and efficacy of PA and AL in patients of both sexes between the ages of 3 months and 10 years who have symptomatic microscopically confirmed acute uncomplicated *Plasmodium falciparum* malaria. Patients will be randomized following a pre-generated randomization code. On the basis of the results of these assessments, the patients will be classified as having therapeutic failure (early or late) or adequate clinical and parasitological response (ACPR). The proportion of patients experiencing therapeutic failure during the follow-up period will be used to estimate the efficacy of the study drug(s). The primary outcome will be PCR-adjusted adequate clinical and parasitological response (ACPR) i.e., absence of patent parasitaemia, regardless of axillary temperature and without evidence of previous treatment failure up to day 28. Secondary outcomes will be adequate clinical and parasitological response without correction for reinfection, parasite clearance time, fever clearance time and the proportions of patients who are aphasitaemic or afebrile on days 1, 2, and 3.

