3.3 Study Site

The study will be conducted in Oni Memorial Children's Hospital, [name]. Ibadan, the capital of Oyo state is a highly populated city located in the rain forest belt of south-western Nigeria. Malaria transmission is intense and occurs all year round in the study area. The total population of Oyo state is estimated to be about 5.5 million with about 3.8 million people in

Ibadan alone. Ibadan has a land mass of 28,245.26 km. Oni Memorial Hospital serves a mix of urban and rural populations as rural patients are referred to it, though more of its patients are from the urban populations.

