attachment)

Where

$Z_{1-\alpha}$ = standard normal deviate for level of significance; at $\alpha=0.05$, it is 1.96

$Z_{1-\beta}$ = standard normal deviate for power (1- β); at $\beta=0.2$ (80% power), it is 0.84 but at $\beta=0.1$ (90%), it is 1.28

P_1 : 28-day cure rate in AL = 96.4%

P_2 : 28-day cure rate in PA = 98.9%

ε : non-inferiority margin= 5%

Applying the formula and parameters above, sample size for each group

90% power: 70 per group [total 140]

80% power: 51 per group [total 102]

Assuming a difference of 2.5% in cure rate between PA and AL (98.9% vs 96.4%) [REF- Roth et al, 2018], 140 patients are required to be 90% sure that the upper limit of a one-sided 95% confidence interval will exclude a difference in favor of the standard group of more than 5%

Total N = 140. Allowing for 20% loss to follow up, the total number of patients required would be 168 to give 84 patients per arm. (See sample size calculation attachment)

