Enrollee will be withdrawn from the study if the parent/care giver withdraws consent, enrollee develop serious concomitant illness or report taking other unauthorized anti-malarial medication apart from the study drugs during the follow-up period. Those who withdraw consent will be revolved back to the hospital care while those who develop serious concomitant illness would have immediate medical care given to them and thereafter be referred for specialist care at Oni memorial children's hospital or University College Hospital, Ibadan at no cost to them. Enrollees who fail treatment with either of the two ACTs being evaluated will receive the alternative ACT under supervision.

Daily checks and corrections will be carried out on the CRF of enrollees seen to ensure correctness and accuracy. Blood samples collected from study participants will be transported to the respective laboratories in the University College Hospital Ibadan for analysis of blood chemistry and hematology parameters the same day they are collected. Efficacy parameters will be evaluated as follows:

- **Efficacy evaluation** will be based on WHO criteria of treatment outcome as follows; (1) Early treatment failure (ETF; danger signs or complicated malaria or failure to adequately respond to therapy on days 0–3); (2) Late clinical failure (LCF; danger signs or complicated malaria or fever and parasitemia on days 4–28 without previously meeting criteria for ETF or LPF); (3) Late parasitological failure (LPF; asymptomatic parasitemia on days 7–28 without previously meeting criteria for ETF or LCF); (4) Adequate clinical and parasitological response (ACPR; absence of parasitemia on day 28 without previously meeting criteria for ETF, LCF, or LPF).
- **Recrudescence** will be defined as the recurrence of asexual parasitemia within 28 days following antimalarial treatment comprising the same genotypes that caused the original illness. This is believed to result from incomplete clearance of asexual parasitemia because of inadequate or ineffective treatment.
- **Parasite clearance time**: time from first dose of ACT until first total and continued disappearance of asexual parasite forms.
- **Fever clearance time**: time from first dose until the first time the body temperature (for those with a raised temperature at enrolment) decrease to below 37.5°C and remain so for at least 24 hours.

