3.7.5 Follow-up of Adverse Events

The healthcare personnel must take all appropriate measures to protect the safety of the patients. Personnel must ensure to document follow-up of the evolution of each adverse event (clinical, biological or other) until resolution or until the stabilization of the patient's status.

All new relevant information concerning the initial SAE shall be recorded on a form "SAE follow-up information form" by the nursing staff of the health centre, and shall be validated by the PI/co-PI who shall transfer the form to the local person/physician responsible for the pharmacovigilance of the project and Shin Poong PV.

In case of a serious adverse event the patient must be followed until complete resolution and normalization of all analysis results, or until chronicity of the patient's status. This can imply that the follow-up of the patient must continue beyond the period of follow-up per protocol, and that additional investigations could be requested.

DATA ANALYSIS.

Data will be entered into the computer using the Epi-data software. This subsequently would be cleaned and transferred to SPSS Statistic Software version 20 for analysis. The outcome of interest (dependent variable) presented as a categorical variable with, presence of malarial parasitemia, and the level of efficacy reported. The independent or explanatory variable of interest in this study would be use of chemotherapy. All independent variable would be reported as categorical. Proportions of treatment outcome will be compared by using chi square. Normally distributed continuous data will be compared using unpaired student t-test. Mean values will be given as mean \pm SD and values of $P < 0.05$ will be considered statistically significant.

ETHICAL CONSIDERATIONS

This study, will be a prospective randomized open label clinical trial comparing the safety and efficacy of Pyronaridine-artesunate and Artemether-lumefantrine in the treatment of symptomatic acute uncomplicated malaria in Nigerian children aged 3 to 144 months who seek treatment in the study hospital. The studies will be conducted according to Good Clinical Practice and the Declaration of Helsinki.

Confidentiality of data: Personal details of enrollees in the study will be treated with utmost confidentiality, as it is against the principles of good clinical practice to make such information public. Also, codes will be assigned to all participants.

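### Crude (PCR-uncorrected) ACPR is compared only as a Day 28 proportion, with no stated role for children followed for part of the 28 days; Kaplan-Meier estimates should be added

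*Combined protocol and SAP*

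**What the plan says.** - **Outcome.** The Study Design section states that "Secondary outcomes will be adequate clinical and parasitological response without correction for reinfection", together with clearance times and early clearance proportions. Section 2.1 also lists crude ACPR as a secondary objective.
- **Definition.** Section 3.7.2 defines ACPR as "absence of parasitemia on day 28 without previously meeting criteria for ETF, LCF, or LPF", so the outcome is a yes/no status at Day 28.
- **Test.** The Data Analysis section says "Proportions of treatment outcome will be compared by using chi square". No Kaplan-Meier estimate, log-rank test, Cox model or censoring rule appears anywhere in the document.
- **Expected difference.** On the WANECAM results, the Rationale says the PCR-corrected outcome is the same for the two drugs, "while PCR uncorrected (new infection) is different and Pyramax is better than AL". Section 3.3 adds: "Malaria transmission is intense and occurs all year round in the study area".
- **Incomplete follow-up.** Section 3.6 sets the total with the words "Allowing for 20% loss to follow up". The case record form has separate outcome codes for withdrawn and for lost to follow-up. No section says how either code enters an analysis, and no analysis population is named.
- **Data available.** Section 3.7.2 schedules smears on Days 7, 14, 21 and 28 and at any unscheduled visit. The case record form holds visit dates and the outcome at each visit.

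**The concern.** Crude ACPR is the efficacy comparison on which the plan's own rationale gives most reason to expect a difference. A child who is smear-negative to Day 21 and then lost has given three weeks of information, yet the plan assigns that child no place in a Day 28 proportion. The analyst must exclude the child or count the child as a failure or a success, and each choice gives a different crude failure rate. If the choice is made after the data are seen, both the reported rates and the arm difference depend on it. The recurrence dates that would avoid the choice are already being collected.

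**Working it through.** **1. The plan's own figures.** The document gives no crude failure rate and no sample size for crude ACPR. Its one calculation sizes the 28-day cure-rate comparison. With P1 = 0.964, P2 = 0.989, margin 0.05 and z values 1.645 and 1.28:

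n = (1.645 + 1.28)² × (0.964×0.036 + 0.989×0.011) / (0.05 + 0.025)² = 8.556 × 0.04558 / 0.005625 = 69.3, so 70 per group.

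This matches the stated 70. The listed 1.96 would give 86, which is a separate matter. Then 140 × 1.2 = 168, or 84 per arm. Only the 84 per arm and the 20% loss are used below.

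**2. Effect of each possible rule for losses.** Assume constant failure and loss rates over 28 days, independent of each other. F is the true Day 28 crude failure (assumed, 5% to 30%) and L = 0.20 is the loss that would occur without failure. Put λ = −ln(1−F) and μ = −ln(1−L).

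- Observed failures: f = λ/(λ+μ) × [1 − (1−F)(1−L)]
- Followed to Day 28 without failure: c = (1−F)(1−L)
- Losses excluded: f/(f+c). Losses as failures: 1−c. Losses as successes: f.

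Worked case F = 0.20: λ = μ, so f = 0.5 × (1 − 0.64) = 0.18 and c = 0.64. Exclusion gives 0.18/0.82 = 22.0%, losses as failures 36%, losses as successes 18%.

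| True failure | Losses excluded | Losses as failures | Losses as successes |
|---|---|---|---|
| 5% | 5.6% | 24% | 4.5% |
| 10% | 11.1% | 28% | 9.0% |
| 15% | 16.6% | 32% | 13.5% |
| 20% | 22.0% | 36% | 18.0% |
| 30% | 32.6% | 44% | 27.1% |

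The errors are +0.6 to +2.6 points, +14 to +19 points, and −0.5 to −2.9 points. At 5% loss, exclusion overstates by only 0.1 to 0.6 points. The arm difference moves too: for a true 20% versus 10%, it reads 22.0 − 11.1 = 10.9 points with exclusion, 36 − 28 = 8 with losses as failures, and 18 − 9 = 9 with losses as successes.

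**3. Failures in later weeks.** Simulation used 84 per arm, detection at Days 7, 14, 21 and 28, 20% loss spread over the visits, and failures weighted to later weeks. Exclusion overstated true failure of 5% to 25% by 0.1 to 0.9 points. A true 30% read as about 31.1%, against 30.0% by Kaplan-Meier. The standard error of the arm difference was 0.071 to 0.072 by Kaplan-Meier and 0.074 by exclusion.

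**4. Power.** Same design, two-sided 5%, 20% loss, assumed rates, chi-square with losses excluded:

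| Day 28 failure, AL vs PA | Timing | Chi-square | Log-rank |
|---|---|---|---|
| 20% vs 10% | same | 38% | 38% |
| 30% vs 18% | same | 38.7% | 38.4% |
| 20% vs 8% | PA later | 56.3% | 59.2% |
| 25% vs 12% | PA later | 52.9% | 57.4% |
| 30% vs 18% | PA later | 40.4% | 46.1% |

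The gain is nil with equal timing and about 3 to 6 points when PA failures are assumed to come later. In the last scenario it is 6.0 points even with no loss (45.4% vs 51.4%), so it comes from the timing assumption and not from recovering partial follow-up.

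**The case against.** A Day 28 proportion is a legitimate pre-stated secondary measure. It fits the WHO outcome categories in section 3.7.2 and the wish in the Rationale to align with the national therapeutic efficacy protocol. The 20% is an allowance, and section 3.7.2 plans reminder calls, home visits and transport fares to reduce it. These points stand: they argue against replacing the proportion, and they make the likely bias smaller than the 20% figures.

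Four stronger readings are tempting, and the documents do not support them.

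- **A reader might infer that the plan overstates crude failure.** That needs a denominator restricted to evaluable children, which the plan never specifies. The sign of the error depends on the missing rule.
- **A reader might infer that PA is expected to delay new infections.** The Rationale says only that "PCR uncorrected (new infection) is different and Pyramax is better than AL" and gives no timing. The background remark on longer post-treatment protection concerns dihydroartemisinin-piperaquine.
- **A reader might infer that chi-square wastes power.** With equal timing there is no gain to be had.
- **A reader might infer that a drug that delays infection is under-credited.** With losses excluded, a true 12.0-point difference with PA later reads as about 12.8. With equal 20% failure by Day 28 and PA later, log-rank rejected in only about 5% to 7% of runs.

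Kaplan-Meier also has a cost: it assumes that loss is unrelated to recurrence. Children withdrawn for taking other antimalarials may well be symptomatic. Excluding losses does not escape this problem, since it too treats them as uninformative.

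**Conclusion.** The point holds as a modest improvement to a secondary analysis. Crude ACPR has one planned comparison, a chi-square on a Day 28 status, and no rule for partial follow-up, while the data for a better estimate are already collected.

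If losses are excluded, crude failure is overstated by about 0.6 to 2.6 points at 20% loss with evenly spread failures, by about 1 point or less with later failures, and by less with less loss. The other two rules give a much larger overstatement or an understatement. Kaplan-Meier is unbiased in these scenarios and slightly more precise. All of this rests on assumed crude rates and on loss independent of recurrence. The case does not rest on power.

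The missing rule for losses also touches the primary PCR-adjusted outcome, which this point does not address.

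**What to change.** In Data Analysis, for the crude outcome:

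1. Add Kaplan-Meier estimates of failure to Day 28 by arm, with the Day 28 difference between arms and its 95% confidence interval, and a log-rank test labelled as supportive.
2. Date each failure by the visit at which it is found. Censor lost or withdrawn children at their last negative smear, or at Day 0 if there is none; the latter covers children withdrawn on the treatment days before any negative smear.
3. Keep the Day 28 crude ACPR proportion alongside, and state its denominator.
4. Report withdrawals for other antimalarial use by arm, so that a reader can judge the independence assumption.

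The cost is a few sentences. The dates and outcome codes are already on the case record form, and no visit, sample or sample-size change is needed. The text should not claim a gain in power.
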